RESEARCH PROTOCOL

Reducing Diagnostic Error to Improve Patient Safety in COPD and Asthma (REDEFINE Study)

Version: 1.5

Date: 1/11/2018

Principal Investigator: [name] MD MPH

Division of Pulmonary, Critical Care, Sleep, and Allergy, Department of Medicine, University of Illinois at Chicago, Chicago, IL

Sponsor: AHRQ 1R01HS024964-01

SPECIFIC AIMS AND HYPOTHESIS

Aim 1: Determine the prevalence of and characteristics associated with diagnostic error (DE) in asthma and/or COPD in an underserved population

Aim 2: Evaluate the effectiveness of the REDEFINE program compared to usual care on health care utilization and patient-centered outcomes (including respiratory medication use, all-cause emergency room visits, and all-cause hospitalizations)

Hypothesis:

The REDEFINE program will reduce health care utilization and improve patient-centered outcomes compared to usual care.

Aim 3: Evaluate the cost impact and cost effectiveness of the REDEFINE program versus usual care

Hypothesis:

The REDEFINE program will be cost-effective in the management of patients with COPD and asthma compared to usual care.

BACKGROUND AND SIGNIFICANCE

Asthma and chronic obstructive pulmonary disease (COPD) are common chronic lung diseases that are diagnosed in more than 30 million adults in the United States.^{1,2} However, diagnostic error (DE), considered one of the most common and harmful of patient-safety problems by the Institute of Medicine,^{3,4} occur frequently with asthma and/or COPD and disproportionately affect minorities and the underserved. DE leads to lost opportunities to identify other chronic conditions, avoidable morbidity and mortality, unnecessary costs to patients and health systems, and poor quality of care.³⁻⁶ Shortness of breath or dyspnea, which is a common symptom in asthma and COPD, is also common for many other chronic conditions such as cardiovascular disease and obesity. A better understanding of the impact of DE and interventions to improve diagnostic accuracy in asthma and COPD are of particular importance for minorities and the underserved that are disproportionately affected by conditions leading to dyspnea.

Spirometry is a simple, mobile, and essential test that is recommended by all major national and international guidelines for the diagnosis of asthma and COPD.⁷⁻¹⁰

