3. SUBJECT SELECTION, RECRUITMENT, AND INFORMED CONSENT

PCP Selection, Recruitment, and Informed consent

Primary care providers (PCPs) specializing in internal medicine or family medicine with at least one half day per week outpatient clinic will be included in the study. We

estimate a total maximum recruitment of 80 eligible PCPs from all sites (approximately 50 PCPs from UI Health and MSHC sites and approximately 30 PCPs from CCHHS). The recruitment will include a combination of paper letter and email invitations with endorsement from the clinic directors and other supervisors. A list of eligible PCPs will be obtained from each site from the clinic directors. A research introduction letter will be mailed to the qualifying practitioners as well as an email invitation sent to their email accounts. The letter and email will be sent simultaneously to ensure contact and will include a short introduction to why the research is being performed and a description of participants' roles in the study. Also included will be a contact number for those who would like to volunteer or who would like additional information. The letter will include a statement that there will be no penalty for not participating. The letter will also contain a postcard with a stamp, where the eligible PCP checks to agree to participate or decline to participate. The email will instruct them to reply by email to the same choices. If a response is not received in 2 weeks, a second recruitment letter and email will be sent followed by a postcard 2 weeks later. Once a PCP agrees to participate, informed consent will be obtained prior to initiation of any study procedures.

Patient Selection, Recruitment, and Informed consent

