Approximately 500 patients will be recruited for this study from the FM, AIM, MSHC and GIM sites (A total of 250 from UI Health and MSHC sites and a total of 250 from CCHHS site). All sites use the same electronic medical record (EMR) system which is Cerner Powerchart. An Information Systems Specialists (ISS) from UI Health (including MSHC) and CCHHS will search the administrative data of their respective sites to provide a list of patients meeting the first three of the inclusion criteria listed above and are scheduled to be seen in PCP clinics or the CRC (Clinical Research Center at UIC), two weeks in the future. More specifically, using electronic health records, within the past 12 months, the following patients will initially be identified: age \geq 40 years and using at least one maintenance respiratory medication (e.g. long acting beta agonists (LABA), long acting anticholinergics (LAA), inhaled corticosteroids (ICS), phosphodiesterase-4 inhibitors (PDE-4i), and at least one of the following 1) diagnosis of asthma (ICD-9 493.xx or ICD 10 J45.xx), 2) diagnosis of COPD, emphysema, or chronic bronchitis (ICD-9 491.xx, 492.xx, 496 or ICD 10 J41.xx, J42.xx, J43.xx, J44.xx). In addition, our ISS will also only include those who have not had a current procedural testing (CPT) codes for spirometry (CPT codes: 94010, 94014, 94015, 94016, 94060, 94070, 94620) or completed order for spirometry testing in the past 3 years.

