4. DESCRIPTION OF PROCEDURES

A) PCP Education and Randomization:

After obtaining PCP informed consent and prior to patient recruitment, a one hour educational session will be held for PCPs participating in the study. The purpose of this session is to provide education to PCPs about COPD, asthma, spirometry, and GOLD and GINA guidelines (GOLD=Global Initiative for Chronic Obstructive Lung Disease, GINA=Global Initiative for Asthma). The educational session will provide continuing medical education credit to those who attend. The learning objectives will be the following: 1) Review COPD and asthma disease definition, presentation, diagnosis and testing including spirometry, 2) be familiar with the GOLD and GINA guidelines and recommendations for therapy.

PCPs who consented to participate in the study and completed the education session will be randomized to have their patients who meet the study criteria receive the intervention or usual care.

B) Patient subject- Intervention:

On the day of the outpatient visit, subjects will be advised to arrive 90 minutes prior to their clinic visit in the same building as the clinic site or the CRC (Clinical Research Center at UIC). The following information will be collected and procedures will be performed:

1. Subject demographic and contact information
2. Co-morbid conditions
3. Smoking history
4. Medication history from patient and also from pharmacy used by subjects
5. A respiratory exacerbation history in the past year
6. Modified Medical Research Counsel (mMRC) dyspnea scale and COPD Assessment Test
7. Quality of life measures
8. Pre and post-bronchodilator (BD) spirometry
9. De-Escalation Spirometry Screener for patients de-escalating based on spirometry (See Based on spirometry findings)
10. De-Escalation Phone Script

Based on spirometry findings:

1. If the spirometry findings are consistent with COPD and/or asthma, the following will be provided to the provider and patient to have available during the clinic visit: a letter summarizing the interpretation of the findings using GOLD/GINA criteria with recommendations for initial guideline driven therapy based on GOLD/GINA guidelines. Subjects will be managed by their PCP thereafter.

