5. STATISTICAL ANALYSES

All data will be stored in a secure, locked location. Data will be entered and managed through the Research Electronic Data Capture (REDCap). REDCap is a secure web-based application for building and managing online databases. REDCap is provided by

the CCTS Design Analysis Core. Data will be analyzed for clinical effectiveness using intention-to-treat principles.⁶⁹⁻⁷¹ For **Aim 1**, we will evaluate the misdiagnosis rates of the intervened and usual care groups separately at the first visit. Then compare rates between groups by using a generalized linear mixed model for binary outcome with two cluster levels, PCP and hospital, to account for the dependence within clusters. For the **Aim 2**, to investigate the impact of the misdiagnosis over time (4 time points: 0, 3, 6, 9, 12 months) on the quality of life and healthcare utilization, we will fit generalized linear mixed models with time, group, and their interaction as the main predictors. Two cluster levels, PCP and hospital, will be specified in the model to account for the dependence within clusters^{72,73} and an appropriate link function will be used for each outcome. Clinical important confounders will also be adjusted in the models. Before these analyses we will use descriptive statistics to describe the sample, and any assumption behind each statistical method will be examined during the analysis. A two-sided p-value less than 0.05 would be considered as statistical significance. All the analyses will be conducted by using SAS 9.2 (SAS Inst., Cary, NC).

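### Aim 2 names no contrast as the REDEFINE effect, models month 0 as a response and does not adjust for the baseline score; the usual default tests are weak for a sustained quality-of-life benefit

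*Combined protocol and SAP*

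**What the plan says.** Section 5 (Statistical Analyses) holds the whole Aim 2 analysis. "we will fit generalized linear mixed models with time, group, and their interaction as the main predictors", and the times are given as "4 time points: 0, 3, 6, 9, 12 months", a count of four against a list of five. On clustering it says "Two cluster levels, PCP and hospital, will be specified in the model to account for the dependence within clusters". Adjustment for clinically important confounders is promised without a list. The decision rule is "A two-sided p-value less than 0.05 would be considered as statistical significance".

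The section does not say whether time is categorical or linear, how group is coded, or which term, visit or contrast is the program effect. No baseline value of the outcome is named as a covariate. The Aim 2 hypothesis is directional: "The REDEFINE program will reduce health care utilization and improve patient-centered outcomes compared to usual care".

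Section 4.E gives the schedule. EQ-5D is taken at baseline and at each three-monthly contact (five points). SF-36 is taken at baseline and at 3, 6 and 12 months (four points). Baseline utilization is a one-year history of ED visits and hospitalizations, while each follow-up value covers the time since the last contact, about three months. Section 4.D makes utilization a primary outcome and quality of life a secondary one.

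**The concern.** Aim 2 asks whether patients under REDEFINE do better than those under usual care after the program starts. The tests that software prints by default for the stated model answer other questions:

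- **Interaction, categorical time:** asks whether the arm difference changes in any way across visits. It spreads the evidence over 4 df (EQ-5D) or 3 df (SF-36).
- **Interaction, linear time:** asks whether the slopes differ. A shift that appears by month 3 and then holds is only partly a slope.
- **Group term, averaged over visits:** gives month 0 equal weight, although the program cannot have acted by then. A sustained effect d appears as 4/5 d = 0.8d (EQ-5D) or 3/4 d = 0.75d (SF-36).
- **Group term, month 0 as reference level:** is the baseline difference between arms.

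Two things are at stake. A real, lasting benefit could be reported as no effect because a weak test was read. And with several candidate tests, one 0.05 threshold and none named in advance, the choice can be made after the results are seen.

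**Working it through.** The documents state no effect size, SD, correlation, ICC, target power or sample-size derivation, so there is no plan figure to reproduce. The check compares tests on the same data at the same effect.

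**Inputs from the documents.** About 500 patients ("Approximately 500 patients will be recruited for this study"); at most 80 PCPs ("estimate a total maximum recruitment of 80 eligible PCPs from all sites"), so m = 500/80 = 6.25 patients per PCP; two-sided 0.05; k = 4 follow-up points for EQ-5D, k = 3 for SF-36.

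**Assumptions.** 1:1 allocation (no ratio is stated); standardized normal outcome; compound symmetry with within-patient correlation ρ = 0.3-0.7; PCP ICC 0-0.05, with a PCP effect constant over time; within-patient correlation correctly modelled; no dropout; effect d at every follow-up visit and none at month 0. The effect is scaled so that the baseline-adjusted follow-up average has 80% power (1-df noncentrality 7.85).

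**Per-patient variances**, with c = (m − 1) × ICC = 5.25 × ICC:
- follow-up mean F = ρ + (1 − ρ)/k + c; month 0 B = 1 + c; covariance C = ρ + c
- baseline-adjusted follow-up average A = F − C²/B
- mean change from month 0 D = (1 − ρ)(1 + 1/k)
- mean of all visits G = ρ + (1 − ρ)/(k + 1) + c

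**Noncentralities.** Mean change: 7.85·A/D on 1 df. Interaction: the same value on k df. Group term: 7.85·(k/(k+1))²·A/G on 1 df. Linear slope, five visits: half the mean-change value, on 1 df.

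**One case in full (EQ-5D, ρ = 0.6, ICC 0.05).** c = 0.2625; F = 0.9625; B = 1.2625; C = 0.8625; A = 0.9625 − 0.8625²/1.2625 = 0.373; D = 0.4 × 1.25 = 0.500; G = 0.6 + 0.08 + 0.2625 = 0.9425.
- Mean change: 7.85 × 0.373/0.500 = 5.86, power 68%.
- Interaction: 5.86 on 4 df, power 46%.
- Group term: 7.85 × 0.64 × 0.373/0.9425 = 1.99, power 29%.
- Slope: 2.93, power 40%.

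If the patient's own baseline enters with a coefficient of 0.6, A is 0.382 and the interaction and group figures become 47% and 30%.

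**EQ-5D schedule, power when the adjusted follow-up average has 80%:**

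| ρ | ICC | Interaction (4 df) | Group term incl. month 0 | Linear slope | Unadjusted mean change |
|---|---|---|---|---|---|
| 0.3 | 0 | 28% | 55% | 26% | 46% |
| 0.5 | 0 | 37% | 43% | 34% | 58% |
| 0.7 | 0 | 47% | 28% | 41% | 69% |
| 0.3 | 0.05 | 35% | 46% | 32% | 55% |
| 0.5 | 0.05 | 42% | 35% | 37% | 64% |
| 0.7 | 0.05 | 50% | 23% | 43% | 71% |

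On the SF-36 schedule (k = 3), over the same ρ and ICC, the interaction has 34-55% and the group term 22-53%.

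**Where the loss comes from.** Degrees of freedom alone take 80% down to 64.5% (3 df) or 59.5% (4 df). The rest comes from leaving out the baseline adjustment. At ICC 0.05, A is below D by 32% at ρ = 0.5 (0.427 v 0.625), 25% at 0.6 and 19% at 0.7 (0.304 v 0.375).

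**Sensitivity.** Under AR(1) correlation 0.3-0.8 without PCP clustering, the interaction has 22-64% and the group term 40-68%. For an effect growing linearly to month 12 (ICC 0, ρ = 0.3/0.5/0.7), the interaction has 53/69/80% and the slope 75/87/93%. At ρ = 0.6 and ICC 0.05 the growing effect gives about 79% and 93%, and an effect present only at months 9 and 12 gives the interaction over 99%.

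**The case against.** The plan lists predictors, not tests. With categorical time, the model contains every arm-by-visit mean, so the follow-up difference is one estimate statement away. A reader might infer that the model cannot give the program effect, or that Aim 2 will be decided by a test with under half the attainable power. The documents support neither: they name no decision test. What is missing is the specification of the right contrast.

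The low figures also depend on effect shape. Section 5 introduces Aim 2 as impact over time, for which an interaction is a natural term, and for growing or late effects the interaction or slope can match or beat the average. A reader might infer that power is lost on every longitudinal Aim 2 outcome; that does not follow. All the figures are for a continuous score, and none covers the primary utilization counts.

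The promised confounder adjustment does not exclude the baseline score, and Aim 3 already compares EQ-5D area under the curve between arms. Neither closes the gap. The baseline score is not named, and the Aim 3 summary serves the cost-utility analysis and is not an Aim 2 test.

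These points limit the claim. The unnamed contrast, month 0 as a response time and the unused baseline score remain.

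**Conclusion.** The concern holds in this limited form, and the plan should be changed. Aim 2 has no pre-specified program-effect contrast, and no usual default test of the stated model estimates the average follow-up difference, whichever coding of time or group is used.

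For a sustained effect on EQ-5D, under compound symmetry with ρ = 0.3-0.7 and PCP ICC 0-0.05, those tests have about 23-55% power where the baseline-adjusted follow-up average has 80%; SF-36 is similar. Even the better choice of an unadjusted mean change reaches only about 46-71%, so naming a contrast without the baseline score still leaves power unused. The exact loss rests on the assumed correlation, ICC and effect shape, none of which the documents give.

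For utilization, the point is one of specification and not of a computed power loss. There is a further reason not to treat month 0 as a response: it is a one-year look-back set beside values of about three months.

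**What to change.** In Section 5, for Aim 2:

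1. **EQ-5D and SF-36:** pre-specify one 1-df contrast each, the average REDEFINE minus usual care difference over the post-baseline assessments, with the patient's own month-0 score as a covariate. Keeping month 0 in the response with the arm means constrained equal there serves the same purpose.
2. **Utilization:** pre-specify the arm difference over the follow-up intervals only. Enter the prior-year ED and hospitalization history as a baseline covariate, not as a month-0 response.
3. **Group-by-time:** keep it as a secondary description of how the effect develops, and state whether time is categorical or linear.
4. **Time points:** reconcile the count of four with the five listed, and note that SF-36 has its own schedule.

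The cost is plan wording; no new patients, visits or data are needed, since the baseline values are already collected. The downside is that a growing or late effect is diluted in the average. The secondary interaction would show it. If the investigators expect that shape, they should say so and choose the contrast to match before the data are seen.

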1. RESEARCH DESIGN

This will be a cluster-randomized comparative effectiveness trial conducted of patients with a primary care provider (PCP) diagnosis of COPD and/or asthma seen in outpatient primary care provider clinics (i.e. Family Medicine, Miles Square Health Center, and Academic Internal Medicine) as well as the CRC (Clinical Research Center) at the University of Illinois Hospital and General Internal Medicine and Family Medicine Clinics

at Cook County Health and Hospitals Systems (CCHHS). Providers will be randomized and their patients who fulfill the inclusion criteria will receive the intervention or be in the usual care group. Adults with a clinician-diagnosed COPD and/or asthma at high risk for diagnostic error due to lack of spirometry will undergo the REDEFINE intervention or usual care based on the PCP randomization. Outcomes will be assessed every 3 months for up to one year.

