- 2. List of current respiratory medications from subject's pharmacy and verification with patient
- 3. Use of diagnostic testing: ECG, echocardiograms, CT/CXR, stress testing, cardiac catheterization, other pulmonary function tests
- 4. Any ED visits or hospitalizations or acute outpatient care visit and associated cause.
- 5. Healthcare utilization outside of U of I system (e.g. testing such as spirometry, ED and hospitalizations) if available through scanned records

3) All subjects will be contacted every 3 months after the initial visit via telephone (T_1 , T_2 , T_3 , T_4) up to one year; or they will be given the option to complete in person based on subject's convenience, for example they have a doctor appointment near time of study follow-up. These phone calls will be used to obtain follow-up data since last study contact. A reminder post-card will be mailed to the subjects a month before the next telephone contact.

- 1. Change in type of health insurance or self-pay

2. List of current respiratory medications from subject's pharmacy and verification with patient
3. Use of diagnostic testing: ECG, echocardiograms, CT/CXR, stress testing, cardiac catheterization, other pulmonary function tests
4. Any ED visits or hospitalizations or acute outpatient care visit and associated cause.
5. Healthcare utilization outside of U of I system (e.g. testing such as ancillary testing, ED and hospitalizations)
6. mMRC
7. A respiratory exacerbation history
8. EQ-5D 5L +B Bolt-on
9. SF-36 short form (at 3, 6 and 12 months)
10. Social support survey (at 6 months and 12 months)

F) Monetary compensation of subjects

1. PCP compensation:

UI Health and MSHC PCPs will receive \$95 in cash after completion of the education session. For CCHHS PCPs, the Division or Department will receive a total of \$95 per participant to be part of the divisional fund to be used by the PCP at their discretion as allowed by their institution.

2. Patient subject compensation:

Baseline visit (Vo):

Same for Intervention and usual care groups: Subjects will be provided \$75 in cash for completing the initial study visit.

Telephone contact (T₁-T₃):

Same for Intervention and usual care groups. Subjects who choose to complete the follow-up in person or via telephone will receive \$20 in cash at the time of the visit or at a later specified time that is convenient for the subject.

Final contact (T₄):

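### The Aim 2 model names PCP and hospital but no within-patient level for repeated outcomes, so its group-by-time standard errors are generally not valid as written

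*Combined protocol and SAP*

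**What the plan says.** Section 1 (Research Design) states: "Outcomes will be assessed every 3 months for up to one year". Section 4.E repeats this for follow-up: "All subjects will be contacted every 3 months after the initial visit via telephone". Under that schedule EQ-5D is collected at baseline and at four contacts (five values), and SF-36 at baseline and months 3, 6 and 12 (four values). Utilization has a prior-year baseline for ED visits and hospitalizations, then four quarterly windows.

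For Aim 2, section 5 says "we will fit generalized linear mixed models with time, group, and their interaction as the main predictors". The visits are given as "4 time points: 0, 3, 6, 9, 12 months", a list of five under a label of four. The dependence structure is then stated: "Two cluster levels, PCP and hospital, will be specified in the model to account for the dependence within clusters".

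Aim 1 compares groups at the first visit, one value per patient, "by using a generalized linear mixed model for binary outcome with two cluster levels, PCP and hospital". The two aims therefore have the same two levels.

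On distribution, the plan says only that "an appropriate link function will be used for each outcome". On model checking it says that "any assumption behind each statistical method will be examined during the analysis", without naming a remedy. No section mentions a patient effect, a covariance over visits or a robust variance.

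**The concern.** Repeated values on one patient are correlated beyond what a shared PCP explains. A model with a PCP intercept and no patient term treats two visits of one patient as if they came from two different patients of that PCP. Stable patient differences cancel out of a within-patient change, but such a model leaves them in the residual that gives the change its standard error. Separately, any tendency of PCPs to differ in how their patients change over time is ignored, which pushes the error the other way.

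The group-by-time term is a main predictor for a primary outcome (utilization) and a secondary one (quality of life). If its standard error is too wide, a real difference in change is missed. If it is too narrow, a difference is declared too easily.

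**Working it through.** **Inputs from the documents.** J = 80 PCPs (the stated maximum) and 500 patients, so m = 500/80 = 6.25 per PCP; T = 5 visits; two-sided 5% test. The plan has no power calculation or standard error to reproduce.

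**Assumed.** 1:1 allocation (40 PCPs and n = 250 patients per arm), equal PCP sizes, complete data, total variance 1, PCP ICC 0.05, within-patient correlation ρ (including the PCP share), PCP-by-time variance v, residual e = 1 − ρ − v.

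**Quality of life, stable correlation.** With A = J(m − 1) = 420, the residual variance that the two-level model estimates is

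s² = [A(T(ρ − ICC) + e) + (J − 2)(T − 1)(mv + e) + A(T − 1)e] / [AT + (J − 2)(T − 1)].

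The variance of the difference between groups in change from baseline to month 12 is 4s²/n as written, against a true 4(v/40 + e/n).

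Example, ρ = 0.5 and v = 0: s² = (1155 + 156 + 840)/2412 = 0.892. As-written SE = √(4 × 0.892/250) = 0.119; true SE = √(4 × 0.5/250) = 0.089; ratio 1.336. Type I error = 2(1 − Φ(1.96 × 1.336)) = 0.9%. Power = Φ(2.80 − 1.96 × 1.336) = 57%.

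| v | ρ = 0.3 | ρ = 0.5 | ρ = 0.7 |
|---|---|---|---|
| 0: SE ratio | 1.145 | 1.336 | 1.699 |
| 0: type I error | 2.5% | 0.9% | 0.1% |
| 0: power in place of 80% | 71% | 57% | 30% |
| 0.04: SE ratio | 1.00 | 1.12 | 1.30 |
| 0.10: SE ratio | 0.86 | 0.92 | 1.01 |
| 0.10: type I error | 9% | 7% | 5% |

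With 50 PCPs and v = 0 the ratios are 1.15, 1.35 and 1.73. REML fits with unequal PCP sizes (20 fits each, some with convergence warnings) gave 1.333 at ρ = 0.5, v = 0 and 0.863 at ρ = 0.3, v = 0.10, in line with the formula.

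**Other contrasts, v = 0.** The month-12 group difference is 7%, 12% and 17% too wide. The time-averaged group difference has ratio 1.00, because the estimated PCP variance takes up the patient variance.

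**AR(1) correlation.** Let R have entries 0.95φ^lag and let ℓ be the contrast over visits. The ratio is √(s² ℓ′ℓ / ℓ′Rℓ), with s² = [A tr R + (J − 2)(tr R − 1′R1/T)]/2412. At φ = 0.5, s² = (420 × 4.75 + 78 × 2.636)/2412 = 0.912. For a linear slope the ratio is √(9.124/11.4) = 0.89; for change to month 12 it is √(1.825/1.781) = 1.01. Over φ = 0.3 to 0.6 the change ratio is 0.99 to 1.04, about right. The slope ratio is 0.89 to 0.92, so its SE is about 8–11% too narrow (type I error 7–8%).

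**Utilization.** The plan names no contrast, so this check uses one of its own: month-12 quarter against the 12-month baseline, at assumed rates of 0.5, 1 and 2 events per patient-year. S = 1/μ₀ + 1/μ₄ is 10, 5 and 2.5, where μ₀ is the 12-month mean and μ₄ the 3-month mean. With stable patient variance p = 1 and no visit-level variance:

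- Poisson: ratio 1.00; simulated type I error 5.0%, 5.1% and 4.8%.
- Negative binomial without a patient level: √((S + 2)/S) = 1.10, 1.18 and 1.34. With patient and visit variances both 1 it is 1.07, 1.11 and 1.14.
- Any-event logit: 1.08, 1.13 and 1.18 (delta method, PCP term ignored).

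**Is a patient intercept alone enough?** No, if v > 0. Its residual is [420e + 78(mv + e)]/498, against a true mv + e.

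- ρ = 0.3, v = 0.04: √(0.699/0.91) = 0.88, type I error about 9%.
- ρ = 0.7, v = 0.10: √(0.298/0.825) = 0.60, about 24%.

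Simulation with unequal PCP sizes (4,000 trials per scenario) gave 10–26% over v = 0.04 to 0.10 and 10–16% for the AR(1) slope. A PCP-level cluster-robust variance with t on 78 df held 4.6–5.4% in all 11 quality-of-life scenarios.

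**The case against.** The plan does not exclude a patient term. It describes clustering by PCP and hospital, and it promises to check assumptions, so an experienced analyst might well add one. That is fair as a forecast. However, the text counts its levels and names them, and they are the levels of the single-visit Aim 1 model. The checking promise leaves the choice until data are in hand, and the obvious addition, a patient intercept alone, can itself be too liberal.

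The large figures sit in a corner. This stands: the 0.1% type I error needs correlation 0.7 and no PCP-by-time variance at all. At v = 0.02 it is 0.4% with 48% power, and at v = 0.04 it is 1.1% with 60%.

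A reader might also infer that the omission inflates false positives for utilization, perhaps to about 22%. The documents do not support that. The 22% arises if one assumes a Poisson model, two events a year, and patient and visit variances of 1: √(2.5/6.5) = 0.62. The cause is unmodelled visit-level overdispersion, which a patient intercept would not absorb. With stable patient differences only, the same Poisson model is calibrated. If the 12-month baseline averages four quarterly draws, the ratio is √(2.5/5) = 0.71 and the figure about 17%. The plan names no Poisson model and no such contrast, and the listed baseline history omits acute outpatient visits.

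**Conclusion.** The point holds for the model as written: the group-by-time standard errors are generally not valid, because within-patient dependence is absent from a longitudinal model. For the quality-of-life change to month 12, under stable correlation of 0.3 to 0.7 and no PCP-by-time variance, they are about 14% to 70% too wide. The excess falls to 0–30% at PCP-by-time variance 0.04. At 0.10 the error runs from 14% too narrow to about right.

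It would be wrong to conclude that every Aim 2 result is affected, or that the error has one direction. The time-averaged group effect is sound, the AR(1) change contrast at 0.3–0.6 is about right, and the utilization result depends on the distribution: Poisson calibrated, negative binomial and logit tending to be too wide.

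Confidence is high on what the text says and on the mechanism. It is lower on size, because every correlation, variance share, rate and dispersion is assumed. The plan should be corrected before analysis.

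**What to change.** In the Aim 2 paragraph of section 5:

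- State the within-patient dependence: a patient-within-PCP random intercept or a residual covariance over visits.
- Pair it with a PCP-by-time term or a PCP-level cluster-robust variance with a small-sample reference distribution. Do not rely on a patient intercept alone.
- Name the group-by-time contrast used for inference and apply this variance to it.
- For utilization, model follow-up counts with a distribution that allows overdispersion and a log person-time offset. Enter the prior-year ED and hospitalization count as a covariate, since it covers 12 months against about 3 per follow-up window.
- As tidying, correct the count of time points.

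The cost is a few sentences and a few lines of code, with no change to visits, recruitment or data collection. Two downsides are small. With about 6 patients per PCP an extra variance component may be estimated at zero, and a robust variance on at most 80 PCPs needs a small-sample correction.
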